9.3. Variables

Unadjusted subject demographic and clinical characteristics and select HCRU and cost characteristics will be described for subjects in the apixaban and LMWH cohorts. Stabilized inverse probability of treatment weighting (IPTW) will be used to adjust for imbalances in measured confounders between the two therapy cohorts. Subject characteristics will then be reported for the therapy cohorts post-IPTW. Post-index economic outcomes of interest (i.e., HCRU and costs) will be evaluated following both IPTW and GLM adjustment.

9.3.1. Baseline Measures

Baseline demographic/clinical characteristics will be descriptively reported for the Apixaban and LMWH cohorts, both pre- and post-IPTW. Demographic characteristics will be measured as of the patient's index date while clinical characteristics will be measured over the 1-year pre-index baseline period.

Demographic Characteristics

- Age (mean, standard deviation [SD], median, interquartile range [IQR])
- Age group (18-24, 25-34, 35-44, 45-54, 55-64, 65-74, ≥ 75 years; n, %)
- Gender (male, female, unknown/missing; n, %)
- Geographic region (Northeast, Midwest, South, West, unknown/missing; n, %)
- Payer type (commercial, Medicaid, Medicare Risk, self-insured, other/unknown; n, %)
- Health plan type (consumer directed health care, health maintenance organization [HMO], indemnity, point-of-service [POS], preferred provider organization [PPO], other/unknown; n, %)

PFIZER CONFIDENTIAL

CT24-WI-GL02-RF02 4.0 Non-Interventional Study Protocol Template For Secondary Data Collection Study 01-Jun-2022

Page 19 of 35

090177e19b7d94e0\Approved\Approved On: 29-Aug-2023 01:40 (GMT)

Apixaban

B0661183 NON-INTERVENTIONAL STUDY PROTOCOL

Protocol Version: 2.0 29 July 2022

- Index date year (2017, 2018, 2019, 2020, 2021; n, %)
- Follow up duration in months (mean, SD, median, IQR)
 - Patients censored due to switching (n, %)
 - Patients censored due to discontinuation (n, %)

Clinical Characteristics

- Prescriber physician specialty (associated with the visit on or closest to the index date, as available) (n, %)
 - Primary care physician (PCP - general practice/family practice/internal medicine)
 - Cardiologist
 - Oncologist
 - Others
 - Unknown/missing
- Index VTE event setting (n, %)
 - Inpatient
 - Total inpatient cost of index VTE hospitalization (mean, SD, median)
 - Length of stay (LOS) of index hospitalization (mean, SD, median)
 - Outpatient
 - Note: Qualifying outpatient encounters followed by qualifying inpatient encounters within 7 days will be considered an inpatient VTE event, unless LMWH or apixaban was initiated between encounters, in which case it will be classified as an outpatient VTE event
- Index VTE type (n, %)
 - DVT
 - PE
 - DVT and PE
- Charlson Comorbidity Index (CCI, Dartmouth-Manitoba adaptation excluding cancer; continuous and categorical [0-1, 2, 3, 4+]) (n, %)
- NCI comorbidity index (continuous and categorical [0-1, 2, 3, 4+]) (n, %)
- Comorbidities of interest (ICD-10 diagnosis codes; n, %)
 - Acquired immune deficiency syndrome (AIDS)
 - Alcohol/drug abuse

PFIZER CONFIDENTIAL

CT24-WI-GL02-RF02 4.0 Non-Interventional Study Protocol Template For Secondary Data Collection Study 01-Jun-2022

Page 20 of 35

090177e19b7d94e0\Approved\Approved On: 29-Aug-2023 01:40 (GMT)

Apixaban

B0661183 NON-INTERVENTIONAL STUDY PROTOCOL

Protocol Version: 2.0 29 July 2022

- Anemia
- Central Venous Catheter
- Cerebrovascular disease
- Coronary heart disease/ischemic heart disease
- Congestive heart failure
- Chronic obstructive pulmonary disease (COPD)
- COVID-19
- Dementia/Alzheimer's disease
- Dyspepsia or stomach discomfort
- Diabetes Mellitis
- Hemiplegia/Paraplegia
- Hematologic disorders associated with bleeding (thrombocytopenia)
- Hyperlipidemia
- Hypertension
- Inflammatory bowel disease
- Liver/Gall bladder/Pancreatic disease
- Obesity
- Peptic ulcer
- Peripheral vascular disease
- Pneumonia
- Renal disease
- Rheumatologic disease
- Sleep apnea
- Spinal cord injury
- Thrombocytopenia
- Thrombophilia
- Varicose veins
- Baseline bleeds (ICD-10 diagnosis or procedure codes, CPT codes, HCPCS codes) (n, %)
- Gastrointestinal
- Intracranial

PFIZER CONFIDENTIAL

CT24-WI-GL02-RF02 4.0 Non-Interventional Study Protocol Template For Secondary Data Collection Study 01-Jun-2022

Page 21 of 35

090177e19b7d94e0\Approved\Approved On: 29-Aug-2023 01:40 (GMT)

Apixaban

B0661183 NON-INTERVENTIONAL STUDY PROTOCOL

Protocol Version: 2.0 29 July 2022

- Others
- History of falls (ICD-10 diagnosis codes) (n, %)
- Fracture/trauma involving lower extremities (ICD-10 diagnosis codes) (n, %)
- Orthopedic/pelvic surgeries (n, %)
- Time (in days) from index VTE encounter date to index date (mean, SD, median, IQR)
- Medications of interest (n, %)
 - Angiotensin-converting enzyme (ACE) inhibitors/Angiotensin receptor blockers (ARB)
 - Antiarrhythmic agents
 - Antiplatelet agents
 - Aromatase inhibitors
 - Beta blockers
 - Erythropoiesis stimulating agents (ESA)
 - Gastroprotective agents
 - Nonsteroidal anti-inflammatory drugs (NSAID)
 - Selective estrogen receptor modulators (SERM)
 - Statins
- Cancer-related variables (measured 6 months prior to the index VTE encounter date until 30 days after the index VTE encounter date)
 - Cancer site (n, %)
 - Bladder
 - Blood (leukemia, lymphoma, multiple myeloma)
 - Brain
 - Breast
 - Gastrointestinal (GI)
 - Upper GI
 - Lower GI
 - Gynecologic
 - Lung
 - Prostate
 - Testicular

090177e19b7d94e0\Approved\Approved On: 29-Aug-2023 01:40 (GMT)

PFIZER CONFIDENTIAL

CT24-WI-GL02-RF02 4.0 Non-Interventional Study Protocol Template For Secondary Data Collection Study 01-Jun-2022

Page 22 of 35

Apixaban

B0661183 NON-INTERVENTIONAL STUDY PROTOCOL

Protocol Version: 2.0 29 July 2022

- Cancer type (n, %)
 - Hematologic cancers
 - Leukemia
 - Lymphoma
 - Multiple myeloma
 - Non-hematologic cancers
- Cancer related treatments (n, %)
 - Chemotherapy
 - Hormone therapy
 - Immunotherapy
 - Radiation
 - Cancer related surgery
- Modified VTE Khorana Risk Scale¹⁰ (n, %)
 - Very high risk (brain, stomach, and pancreas)
 - High risk (lung, lymphoma, gynecologic, bladder, testicular and renal cell carcinoma)
 - Other cancers

Baseline HCRU and costs

- Patients with a pre-index hospitalization (n, %)
- Patients with a pre-index emergency room (ER) visit (n, %)
- Patients with a pre-index outpatient physician office visit (n, %)
 - Number of pre-index outpatient physician office visits (mean, SD, median, IQR)
- Total all-cause healthcare costs (mean, SD median, IQR)
 - Inpatient
 - Outpatient medical
 - ER
 - Pharmacy

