9.1.1. Inclusion criteria

Patients must meet all of the following inclusion criteria to be eligible for inclusion in the study:

090177e19b7d94e0\Approved\Approved On: 29-Aug-2023 01:40 (GMT)

Apixaban

B0661183 NON-INTERVENTIONAL STUDY PROTOCOL

Protocol Version: 2.0 29 July 2022

1. Patients with ≥ 1 diagnosis code for VTE (inpatient [primary or secondary discharge diagnosis] or any position on an outpatient non-ancillary medical claim) between January 1, 2017 and October 31, 2021 (selection window).
 - Note: Qualifying outpatient encounters followed by qualifying inpatient encounters within 7 days will be considered an inpatient VTE event, unless LMWH or apixaban was initiated between encounters, in which case it will be classified as an outpatient VTE event
 - First date of claim with a VTE diagnosis code will be termed the ‘index VTE encounter’

2. Evidence of having active cancer, defined as ≥ 2 medical claims with a cancer diagnosis (excluding nonmelanoma skin cancer) on different days during the 6 months before or within 30-days after the index VTE event

OR

≥ 1 medical claim for a cancer diagnosis AND ≥ 1 claim for cancer treatment (eg: chemotherapy, radiation, immunotherapy, hormone therapy or cancer related surgery using national drug codes (NDC), international classification of diseases, tenth revision, clinical modification [ICD-10-CM] procedure codes or healthcare common procedure coding system [HCPCS] codes) during 6 months before or within 30 days after the index VTE encounter

3. ≥ 1 claim of apixaban or LMWH (dalteparin orenoxaparin) on or within 30 days following the index VTE encounter.
 - a. The date of the first apixaban or LMWH prescription fill will be designated as the index date
4. ≥ 12 months of continuous enrollment prior to the index date (pre-index)
5. ≥ 1 months of continuous enrollment including and following the index date (post-index)
 - a. Note: Each patient will have a variable follow-up period with a minimum of 1-month follow-up. Patients will be followed from the day after the index date through the earliest of the following: health plan disenrollment, index therapy discontinuation, switch to another anticoagulant, or study end (December 31, 2021).
 - b. Discontinuation will be defined as occurrence of a ≥ 30 day gap from the run-out of days’ supply of the index LMWH or apixaban prescription. The date of the discontinuation will be defined as the last day of the days’ supply of the last filled prescription.

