9.7. Data analysis

Descriptive statistics will be produced for all relevant study measures previously described, for the 2 therapy cohorts of interest. Categorical measures will be presented using frequency (number of patients [n]) and percentage (%) of total study patients observed in each category. Continuous and count variables will be presented as the mean, SD, median and IQR. As relevant, continuous variables will also be categorized into intervals.

Stabilized IPTW will be used to balance patient characteristics between apixaban and LMWH cohorts.^{11,12} Weights will be constructed by estimating each subject's probability of receiving treatment based on covariates. For comparisons of baseline characteristics between the apixaban and LMWH cohorts, both pre- and post-IPTW, standardized mean difference (SMD) will be calculated to evaluate the difference in baseline covariates between cohorts. SMD is calculated as the difference in means or proportions of a variable divided by the pooled standard deviation. SMD of ≥ 0.10 between groups is considered meaningful.¹³ For comparisons of events and HCRU/cost over the variable post-index period post-IPTW, comparisons will be conducted using weighted chi-square tests for categorical variables and weighted t-tests (mean) for continuous variables (note there is no corresponding weighted test for the median). Comparisons between independent samples (e.g., among patients with ≥ 1 hospitalization) and pre-IPTW samples will be conducted using the parametric t-test (mean) and non-parametric Wilcoxon rank-sum test (median) for continuous variables; data will be reported for the unweighted sample. A p-value < 0.05 will be considered statistically significant. However, to account for multiple comparisons, a Bonferroni correction may be implemented such that the critical p-value ($p < .05$) may be divided by the number of comparisons (i.e., 3 comparisons, in order to yield a new critical p-value, $.05/3 = 0.0167$). Analyses will be conducted using SAS[®] (statistical analysis software) Release 9.4 (SAS Institute Inc., Cary, NC).

IQVIA will develop up to 4 multivariable analysis models, to be mutually agreed upon Pfizer/BMS and IQVIA. For example these may include weighted generalized linear models (GLM) with log transformation and gamma distribution to estimate adjusted (all-cause) cost ratio

PFIZER CONFIDENTIAL

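### Cancer treatments are recorded as baseline up to 30 days after the VTE encounter, so the window runs past the index date and may bring post-index care into the adjustment

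*Combined protocol and SAP*

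**What the plan says.** Section 9.3.1 sets a general rule: "clinical characteristics will be measured over the 1-year pre-index baseline period". The Abstract (Variables) and Section 9.1 agree with it. The first places explanatory variables before or on the index date, and the second measures baseline characteristics in the 12 months before it.

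Later in Section 9.3.1 a different window is given for one group: "Cancer-related variables (measured 6 months prior to the index VTE encounter date until 30 days after the index VTE encounter date". The group holds cancer site, cancer type, a modified Khorana risk grouping and five cancer treatments (chemotherapy, hormone therapy, immunotherapy, radiation, cancer-related surgery).

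Section 9.1.1 fixes the timing. The qualifying fill must occur "on or within 30 days following the index VTE encounter", and "The date of the first apixaban or LMWH prescription fill will be designated as the index date". Outcomes begin straight afterwards: "Patients will be followed from the day after the index date through the earliest of the following" of several censoring events.

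On adjustment, Section 9.7 says "Stabilized IPTW will be used to balance patient characteristics between apixaban and LMWH cohorts" and "Weights will be constructed by estimating each subject's probability of receiving treatment based on covariates". No list of those covariates is given. The outcome models in Section 9.7 draw on demographic and clinical characteristics. The total all-cause cost in Section 9.3.2 adds pharmacy, outpatient and inpatient cost, with no exclusion for cancer care.

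**The concern.** The cancer window is anchored on the VTE encounter, while the outcome period is anchored on the fill. Whenever the fill comes before day 30, cancer treatment given after anticoagulation began can be recorded as a baseline characteristic. The same claims are also counted as post-index cost.

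Adjusting for care that follows the start of treatment causes two problems. If the anticoagulant influences the timing or use of early cancer treatment, weighting on that treatment removes part of a real cost difference and can introduce selection bias. Even if it does not, merging pre-index and post-index treatment into one flag weakens control of the pre-index treatment, which is the true confounder. The comparison at stake is the first primary objective, all-cause cost per patient per month (PPPM).

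**Working it through.** The plan gives no figure on this point to reproduce. Its cohort sizes (1,788 and 1,867) concern recurrent VTE and do not depend on the covariate window.

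**Step 1: overlap in days.** Inputs: the window ends on day 30 after the VTE encounter (Section 9.3.1); the index date is day d, from 0 to 30 (Section 9.1.1); follow-up starts on day d + 1 (Section 9.1.1). Overlap = 30 − d.

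| Fill on day d | 0 | 3 | 7 | 14 | 29 | 30 |
|---|---|---|---|---|---|---|
| Window days after index | 30 | 27 | 23 | 16 | 1 | 0 |

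Of the 31 permitted index days, 30 give some overlap. The documents do not give the distribution of time from VTE to fill. If it were uniform (assumption), the mean overlap would be 15 days. For a day-0 fill with the one-month minimum of follow-up, the window covers essentially the whole outcome period.

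**Step 2: share of the whole window.** Taking 6 months as 183 days (assumption), the window is 183 + 30 = 213 days. The post-index share is 30/213 = 14% at d = 0, 23/213 = 11% at d = 7 and 15/213 = 7% at d = 15.

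**Step 3: who is affected.** The treatments are reported as counts and percentages, so they are read here as yes/no flags. A patient treated earlier in the window, before the index date, is coded yes either way. Only patients whose first in-window treatment falls after the index date change category.

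**Step 4: whether it can matter.** The table shows a simulation in which every input is assumed: 40% with pre-index chemotherapy, who are less likely to receive apixaban; $6,000 per post-index course; an unmeasured severity that raises both early chemotherapy and cost; and a direct apixaban effect of −$500. Entries are apixaban minus LMWH in dollars per patient, not PPPM.

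| Assumed drug effect on early cancer treatment | Truth | Weights on pre-index treatment | Weights on any treatment in the stated window | Error of the latter |
|---|---|---|---|---|
| none | −500 | −499 | −442 | +58 |
| −5 points | −799 | −796 | −541 | +258 |
| +5 points | −200 | −204 | −349 | −149 |
| +10 points | +98 | +99 | −260 | −358 |

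With no drug effect, the $58 error comes from the merged flag: keeping pre- and post-index treatment as separate variables gives −$496. The table shows that the error can go either way and can change the sign. It does not estimate the bias in this study.

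**Step 5: after the change.** If the treatment window ends on the index date, the overlap is 0 days for every patient.

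**The case against.** The strongest objection is that nothing in the plan says these variables enter the weights. Section 9.3.1 is a reporting list. It cannot be the propensity set as it stands, because it also contains follow-up duration and censoring reasons. A reader might infer that the protocol commits to weighting on post-index care, but the documents do not go that far. Entry into the models remains an inference. It is a reasonable one: Section 9.3 aims the weights at measured confounders, cancer treatment is an obvious one, these characteristics are reported before and after weighting, and nothing excludes them from the weights or the outcome models.

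Second, the parenthetical window may be a deliberate exception, since it matches the active-cancer criterion in Section 9.1.1. That may explain its origin, but no reason is given for using an eligibility window for covariates, and intent does not remove the overlap.

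Third, the bias needs a mechanism that the documents do not describe. Nothing in them shows that anticoagulant choice changes cancer care within 30 days, and most of the window is pre-index in any case. This stands, and it limits what can be said about size.

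Fourth, ending the window at the index date for every cancer variable would go too far. Site, type and risk group are attributes of the disease. Patients who become eligible on post-index claims would be left without a category. This also stands.

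**Conclusion.** The concern holds in a limited form. The overlap of 30 − d days for every fill before day 30 follows directly from the text, as does the departure from the pre-index rule. If cancer treatments enter the propensity or outcome models with the stated window, the primary cost comparison can be biased through patients whose treatment is first recorded after the index date. That condition is likely but not documented.

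The documents support no dollar figure. A reader might multiply an assumed 10-point cohort difference in early treatment by an assumed $15,000 per course and conclude that 0.10 × $15,000 = $1,500 per patient is suppressed. Neither input is in the documents. The result is not on the plan's PPPM scale, where it would be $1,500 at 30 days of follow-up, $500 at 90 and $250 at 180. Full suppression would also require that the drug causes the whole difference and that the flag captures all of it. Any part that reflects existing patient differences is confounding that the weights ought to remove. The direction is equally unknown, and the bias may be small.

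**What to change.** In Section 9.3.1, state that for any propensity score or outcome model, cancer-related treatments are measured from 6 months before the index VTE encounter through the index date only. Reconcile the general pre-index rule with the cancer window in the same section, and state in Section 9.7 which cancer variables enter the models.

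Cancer site, type and risk grouping may keep the eligibility window, so that every eligible patient can be classified. Add a sensitivity analysis limited to patients who meet the active-cancer criterion by the index date.

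The cost is a short text change and one extra analysis. The required sample size does not change. The downside is that some patients whose treatment starts just after the index date will be coded as untreated at baseline.

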- To compare HCRU associated with recurrent VTE, major bleeding, and CRNM bleeding among VTE patients with cancer treated with apixaban vs LMWH

Study design

A retrospective database analysis will be conducted using IQVIA's PharMetrics® Plus database among newly diagnosed VTE patients with active cancer who received apixaban or a LMWH on or within 30 days following the VTE diagnosis. The analysis will be conducted using data from 01 January 2016 through 31 December 2021 (i.e., the *study period*), including a 12-month pre-index period and 1-month post-index period and patients will be followed through the earliest of the following: health plan disenrollment, index therapy discontinuation, switch to another anticoagulant or end of study period.

Population

Adult patients with evidence of cancer and newly diagnosed VTE, followed by a claim of apixaban or LMWH will be identified. The date of the first apixaban or LMWH prescription will be termed as the index date and two cohorts will be identified based on this index prescription. Patient will be continuously enrolled during the 12-month pre-index period and with a variable post-index period. Other exclusion criteria will also be applied such as patients with evidence of atrial fibrillation, mechanical heart valve, inferior vena cava filter, antiphospholipid syndrome, pregnancy and with any data quality issues.

Variables*Exposures and explanatory variables in the pre-index period or on index date:*

- Demographic characteristics
- Clinical characteristics
- Baseline HCRU and costs

Outcomes

- All-cause HCRU and costs
- Recurrent VTE related HCRU and costs
- Major bleeding related HCRU and costs
- CRNM bleeding related HCRU and costs

Data sources

IQVIA's PharMetrics® Plus database comprises adjudicated claims for more than 190 million unique enrollees across the United States (US). Enrollees with both medical and pharmacy coverage in 2020 represented 40 million lives. PharMetrics Plus has diverse representation of

PFIZER CONFIDENTIAL

CT24-WI-GL02-RF02 4.0 Non-Interventional Study Protocol Template For Secondary Data Collection Study 01-Jun-2022

Page 9 of 35

090177e19b7d94e0\Approved\Approved On: 29-Aug-2023 01:40 (GMT)

Apixaban

B0661183 NON-INTERVENTIONAL STUDY PROTOCOL

Protocol Version: 2.0 29 July 2022

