9.1. Study period and study design

The analysis will be conducted using data from 01 January 2016 through 31 December 2021 or the latest available data at the time of extraction (i.e., the *study period*). Patients will be identified during a *selection window* of 01 January 2017 to 31 October 2021. The date of the first apixaban or LMWH prescription on or within the 30 days following a VTE diagnosis will be termed as the index date. Patients will be required to have continuous enrollment with medical and pharmacy benefits for 12-months prior to the index date to assess study eligibility criteria and to measure baseline characteristics (*the baseline or pre-index period*). Patients will also be required to have continuous enrollment with medical and pharmacy benefits for at least one month (30 days) starting on and following the index date (the follow-up or post-index period) and will be followed through the earliest of the following: health plan disenrollment, index therapy discontinuation, switch to another anticoagulant (includes switch to the other study medication or unfractionated heparin, fondaparinux, warfarin, rivaroxaban, dabigatran, or edoxaban), or end of study period (31 December 2021).

Note: Patients in the LMWH cohort will NOT be considered to have discontinued or switched if they change to an LMWH other than the index LMWH (dalteparin, enoxaparin, or tinzaparin).

Figure 1. Study Period

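### Baseline hospital use and cost run up to the index fill and include the index VTE encounter, so the pre-index hospitalization flag and its SMD can misstate earlier hospital use

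*Combined protocol and SAP*

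**What the plan says.** Three definitions combine.

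- **Index date.** Section 9.1.1, criterion 3: "The date of the first apixaban or LMWH prescription fill will be designated as the index date". The fill must fall "on or within 30 days following the index VTE encounter".
- **Baseline window.** Section 9.1 requires enrollment for "12-months prior to the index date to assess study eligibility criteria and to measure baseline characteristics". Section 9.3.1 repeats that "clinical characteristics will be measured over the 1-year pre-index baseline period".
- **Baseline HCRU and costs.** Section 9.3.1 lists "Patients with a pre-index hospitalization (n" as a yes/no item without a count, a yes/no ER item, an office-visit item with a count, and total all-cause cost split into inpatient, outpatient medical, ER and pharmacy. No text there or elsewhere takes the index VTE encounter out of these items.

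The same section lists the VTE episode separately: setting, "Total inpatient cost of index VTE hospitalization (mean, SD, median", length of stay, and days from VTE to index. The Abstract places baseline HCRU and costs under "Exposures and explanatory variables in the pre-index period or on index date".

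Section 9.7 treats an SMD of 0.10 or more as meaningful for balance and uses the same cut-off to retain covariates in the regression models. It does not list the covariates that enter the weights.

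**The concern.** Hospital use before the VTE is one of the available markers of how sick a cancer patient already was, and therefore of later all-cause cost, a primary outcome. A flag that the index VTE admission itself can switch on mixes two things: whether the VTE was treated in hospital, and whether the patient had been admitted before. For a patient with an inpatient VTE before the fill, only the first remains visible.

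If the cohorts differ in earlier admissions, the SMD for this flag may not show it. The reader of the balance table could be falsely reassured, or misled about direction. A flag whose SMD falls below 0.10 could also be left out of the regression models under the retention rule in section 9.7.

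**Working it through.** **No plan figure to reproduce.** The documents give no hospitalization rates, inpatient-VTE shares or time-to-fill distribution. The only calculated design figures, 1,788 and 1,867 patients per cohort (section 9.5), reproduce with the pooled-variance two-proportion formula but do not bear on this point.

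**Step 1: timing.** Let the VTE encounter be day 0 and the fill day d, with d from 0 to 30. The window ends at day d. If d > 0, day 0 lies inside it, so an admission on day 0 sets the flag to yes. If d = 0, a strictly prior window would leave the encounter out. A stay that spans the fill is not addressed.

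**Step 2: what the flag measures.** Let s be the share of a cohort with an inpatient VTE before the fill, and h the true rate of hospitalization before the VTE. Assuming s and h are independent:

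- flag rate f = s + (1 − s) × h
- SMD = (f_L − f_A) / √{[f_A(1 − f_A) + f_L(1 − f_L)] / 2}, with L for LMWH and A for apixaban

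**Step 3: equal inpatient shares.** Assume h_A = 0.35 and h_L = 0.45. The true SMD is 0.10 / √[(0.2275 + 0.2475)/2] = 0.10 / 0.487 = 0.205.

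| s (both cohorts) | f_A | f_L | SMD of flag |
|---|---|---|---|
| 0.30 | 0.30 + 0.70 × 0.35 = 0.545 | 0.30 + 0.70 × 0.45 = 0.615 | 0.142 |
| 0.50 | 0.675 | 0.725 | 0.109 |
| 0.70 | 0.805 | 0.835 | 0.078 |

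In the last row a true SMD of 0.205 falls below the plan's 0.10.

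**Step 4: other assumed rates, equal shares of 30%, 50% and 70%.**

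- 30% vs 40%: true SMD 0.211; flag 0.141, 0.107, 0.076.
- 25% vs 30%: true SMD 0.112; flag 0.070, 0.052, 0.036, below 0.10 throughout.

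**Step 5: unequal shares, with h of 30% vs 40%.**

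- s_A = 0.50, s_L = 0.40: f_A = 0.650, f_L = 0.640, SMD −0.021. The sign reverses.
- s_A = 0.40, s_L = 0.50: f_A = 0.580, f_L = 0.700, SMD 0.252. The imbalance is exaggerated.

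Dilution is therefore one case among several. What holds generally is that the flag's SMD is not the SMD of earlier hospital use.

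**The case against.** Measuring covariates up to treatment start is a coherent choice. The VTE stay is pre-treatment, and adjusting for it is legitimate. Because a secondary discharge diagnosis qualifies, the stay may itself be a cancer admission that carries severity information. This stands, and it is why the episode should be kept as its own covariates and not discarded.

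A reader might infer that earlier hospital history becomes invisible for every inpatient-VTE patient. The documents do not support that. The saturation affects yes/no flags only, and only where the encounter precedes the fill. Baseline costs are continuous and still contain earlier inpatient spending. Since index-stay cost is listed separately, earlier inpatient cost can be obtained by subtraction for stays wholly before the fill. Office visits have a count. Comorbidities, cancer site, type and treatments also remain.

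A reader might also infer a definite bias in the primary cost comparison. If the weights used only VTE setting and this flag, the assumed 10-point difference would persist among inpatient-VTE patients, leaving s × 10 = 3, 5 or 7 points overall. At an assumed $4,000 per patient per month for prior hospitalization, that is 0.03, 0.05 or 0.07 × 4,000 = $120, $200 or $280. Those inputs are all assumed, the two-covariate model is not the plan's, and section 9.3 adds GLM adjustment. The documents do not establish which variables enter the weights; the table shells and code files are stand-alone documents and could hold more detail. The figures are illustrative only.

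**Conclusion.** The concern holds for the window and the flags. As written, an inpatient index VTE before the fill makes the hospitalization flag yes whatever the earlier history, and its cost enters a baseline total alongside a separate entry for the same stay. The ER and office-visit flags share the problem; for office visits the count softens it.

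The consequence that can be shown is for the SMD, which serves both as balance check and as retention rule. Under the assumed rates, a true 0.205 appears as anything from 0.142 to 0.078 at equal inpatient shares of 30% to 70%. The size depends on those rates, on the shares and on independence between VTE setting and earlier admission. The direction is not fixed, because unequal shares can reverse or inflate the SMD. How much reaches the primary cost comparison cannot be determined from the documents. This is a cheap improvement to the plan and does not show that its result will be biased.

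**What to change.** In section 9.3.1:

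1. Measure baseline hospitalization, ER visits, office visits and all-cause costs from 12 months before the index date to the day before the index VTE encounter.
2. Keep the index VTE episode as separate covariates: setting, stay cost, length of stay, days from VTE to index, and any other use between the VTE encounter and the fill.
3. Use both sets in the propensity model and in the SMD table, and list the propensity covariates in section 9.7.

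The cost is a sentence or two of text and a changed end date in the baseline program. The prior-use window becomes up to 30 days shorter than 12 months and varies with each patient's time to fill. Enrollment requirements and sample size do not change.
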